3.2 Number of Subjects

20-87 patients

3.3 Eligibility Criteria

Patients must have baseline evaluations performed prior to the first dose of study drug and must meet all inclusion and exclusion criteria. In addition, the patient must be thoroughly informed about all aspects of the study, including the study visit schedule and required evaluations and all regulatory requirements for informed consent. The written informed consent must be obtained from the patient prior to enrollment. The following criteria apply to all patients enrolled onto the study *unless otherwise specified*.

3.3.1 Inclusion Criteria

1. Pre and postmenopausal women or men with stage IV ER+ breast cancer histological or cytological confirmation

ER-positive tumors

- a. Progressed after at least one line of hormonal therapy

- b. Any number of prior chemotherapy in the metastatic setting
- c. Any number of prior hormonal therapies.
- d. HER2 positive or negative

ER-negative tumors

- e. PD-L1 low, high or unknown
 - f. Progression after prior PD-1 or PD-L1 inhibitors allowed
 - g. HER2 positive or negative
2. 18 years or older.
 3. Eastern Cooperative Oncology Group (ECOG) Performance Status of ≤ 2 .
 4. Understand and voluntarily sign an informed consent prior to any study-related assessments or procedures are conducted and are able adhere to the study visit schedule and other protocol requirements.
 5. Consent to paired tumor biopsy, for accessible tumors
 6. Measureable tumor by RECIST criteria v.1.1
 7. Per Good Clinical Practice, any toxicity related to prior therapies that, in the opinion of the investigator, would potentially be worsened with anti-PD1 therapy should be resolved to less than Grade 1
 8. Adequate organ function within 14 days of study start:
 - o Absolute neutrophil count (ANC) $\geq 1.5 \times 10^9/L$
 - o Hemoglobin (Hgb) $\geq 9g/dL$ (may transfuse if clinically indicated)
 - o Platelets (plt) $\geq 100 \times 10^9/L$
 - o Potassium within normal range, or correctable with supplements;
 - o AST and ALT $\leq 2.5 \times$ Upper Limit Normal (ULN) or $\leq 5.0 \times$ ULN if liver tumor is present;
 - o Serum total bilirubin $\leq 1.5 \times$ ULN
 - o Serum creatinine $\leq 1.5 \times$ ULN, or 24-hr clearance $\geq 60ml/min$; and
 9. Females of child-bearing potential (defined as a sexually mature women who):
 - o Has not undergone a hysterectomy (the surgical removal of the uterus) or bilateral oophorectomy (the surgical removal of both ovaries) or,
 - o Has not been naturally postmenopausal for at least 24 consecutive months (i.e., has had menses at any time during the preceding 24 consecutive months).

Must have negative serum pregnancy test within 7 days before starting study treatment in females of childbearing potential (FCBP) and willingness to adhere to acceptable forms or birth control (a physician- approved contraceptive method (oral, injectable, or implantable hormonal contraceptive; tubal ligation; intra-uterine device; barrier contraceptive with spermicide; or vasectomized partner).
 10. Male subjects with female partner of childbearing potential must agree to the use of a physician-approved contraceptive method throughout the course of the study

3.3.2 Exclusion Criteria

1. Any significant medical condition, laboratory abnormalities, which places the subject at unacceptable risk if he/she were to participate in the study.
2. Has had prior chemotherapy, targeted small molecule therapy, or radiation therapy within 2 weeks prior to study Day 1 or who has not recovered (i.e., \leq Grade 1 or at baseline) from adverse events due to a previously administered agent.
 - a. Note: Subjects with \leq Grade 2 neuropathy are an exception to this criterion and may qualify for the study.
 - b. Note: If subject received major surgery, they must have recovered adequately from the toxicity and/or complications from the intervention prior to starting therapy.
 - c. Patients may continue on ovarian suppression
3. Has a known additional malignancy that is progressing or requires active treatment. Exceptions include basal cell carcinoma of the skin, squamous cell carcinoma of the skin, or in situ cervical cancer that has undergone potentially curative therapy.
4. Any condition that confounds the ability to interpret data from the study.
5. Symptomatic central nervous system metastases. Subjects with brain metastases that have been previously treated with WBXRT and are stable for 6 weeks are allowed. Gamma or cyber knife treated lesions may enroll 2 weeks after completion if toxicities are resolved and no longer requiring steroids, patients with asymptomatic brain metastases are allowed after discussion with the study sponsor.)
6. Persistent diarrhea or malabsorption \geq NCI CTCAE grade 2, despite medical management.
7. Unstable angina, significant cardiac arrhythmia, or New York Heart Association (NYHA) class 3 or 4 congestive heart failure.
8. Prior systemic cancer-directed treatments or investigational modalities \leq 5 half-lives or 3 weeks, whichever is shorter, prior to starting study drug or who have not recovered from side effects of such therapy (except alopecia).
9. Has an active auto-immune disease requiring systemic treatment within the past 3 months or a documented history of clinical autoimmune disease in the past, or a syndrome that requires systemic steroids or immunosuppressive agents. Subjects with vitiligo or resolved childhood asthma/atopia would be an exception to this rule. Subjects that require intermittent use of bronchodilators or local steroid injections would not be excluded from the study. Subjects with hypothyroidism stable on hormone replacement or Sjorgen's syndrome will not be excluded from the study.
10. Has evidence of interstitial lung disease or active, non-infectious pneumonitis.
11. Has an active infection requiring systemic therapy.
12. Has a history or current evidence of any condition, therapy, or laboratory abnormality that might confound the results of the trial, interfere with the subject's participation for the full duration of the trial, or is not in the best interest of the subject to participate, in the opinion of the treating investigator.
13. Has known psychiatric or substance abuse disorders that would interfere with cooperation with the requirements of the trial.

14. Is pregnant or breastfeeding, or expecting to conceive or father children within the projected duration of the trial, starting with the pre-screening or screening visit through 120 days after the last dose of trial treatment. Pregnant women are excluded from this study because vorinostat, tamoxifen and PD-1 are drug classes with the potential for teratogenic or abortifacient effects. Because there is an unknown but potential risk for adverse events in nursing infants secondary to treatment of the mother, breastfeeding should be discontinued if the mother is treated with vorinostat, tamoxifen and PD-1 inhibitors.
15. Active and ongoing steroid use, except for non-systemically absorbed treatments (such as inhaled or topical steroid therapy for asthma, COPD, allergic rhinitis).
16. Major surgery \leq 2 weeks prior to starting a study drug or who have not recovered from side effects of such therapy.
17. Known hypersensitivity to pembrolizumab or any of its ingredients.
18. Has received a live vaccine within 30 days prior to the first dose of trial treatment.

3.4 Duration of Therapy

In the absence of treatment delays due to adverse events, treatment may continue for 24 months or until:

- Clearly documented disease progression
- Inter-current illness that prevents further administration of treatment
- Unacceptable adverse event(s)
- Patients decides to withdraw from the study
- Significant patient non-compliance with protocol
- General or specific changes in the patients' condition render the patient unacceptable for further treatment in the judgment of the investigator.
- Patients may receive palliative radiation therapy for isolated symptomatic lesions

A subject must be discontinued from the trial for any of the following reasons:

- The subject or legal representative (such as a parent or legal guardian) withdraws consent.
- Confirmed radiographic disease progression

Note: For unconfirmed radiographic disease progression, but clear clinical progression in the opinion of the treating physician or investigator, the patient should be withdrawn from study for progression.

Note: A subject may be granted an exception to continue on treatment with confirmed radiographic progression if clinically stable or clinically improving by symptoms or tumor markers.

Unacceptable adverse experiences as described in Section 7.4

- Intercurrent illness that prevents further administration of treatment
- Investigator's decision to withdraw the subject
- The subject has a confirmed positive serum pregnancy test

- Noncompliance with trial treatment or procedure requirements
- The subject is lost to follow-up

3.5 Duration of Follow Up

Patients will be followed for 30 days after completion of treatment or removal from study. Patients removed from study for unacceptable treatment related adverse event(s) will be followed until resolution or stabilization of all treatment related adverse events to Grade 2 or lower.

Subjects who discontinue for reasons other than progressive disease will have post-treatment follow-up for disease status until disease progression, initiating a non-study cancer treatment, withdrawing consent or becoming lost to follow-up. After documented disease progression each subject will be followed by telephone for overall survival until death, withdrawal of consent, or the end of the study, whichever occurs first.

Subjects may withdraw consent at any time for any reason or be dropped from the trial at the discretion of the investigator should any untoward effect occur. In addition, a subject may be withdrawn by the investigator or the Sponsor if enrollment into the trial is inappropriate, the trial plan is violated, or for administrative and/or other safety reasons. Specific details regarding discontinuation or withdrawal are provided in Section 6.2.7

3.6 Randomization Procedures

This is an open-label randomized trial; therefore, the Sponsor, investigator and subject will know the treatment administered. Two arms will be tested, with each independent assessment. Patients will be randomized to either arm using a computerized randomization program by [name]. Patients will be further stratified by prior number of chemo- and hormonal therapies.

No randomization is required for ER-negative patients (patients must have biopsiable disease)

3.7 Study Timeline

Trial treatment should be administered on Day 1 of each cycle after all procedures/assessments have been completed as detailed on the Trial Flow Chart (Section 5.1). Trial treatment may be administered up to 3 days before or after the scheduled Day 1 of each cycle due to administrative reasons. All trial treatments will be administered on an outpatient basis. pembrolizumab will be administered as a 30 minute IV infusion (treatment cycle intervals may be increased due to toxicity as described in Section 5.2.1.2). Sites should make every effort to target infusion timing to be as close to 30 minutes as possible. However, given the variability of infusion pumps from site to site, a window of -5 minutes and +10 minutes is permitted (i.e., infusion time is 30 minutes: -5 min/+10 min)

3.7.1 Clinical Criteria for Early Trial Termination

Early trial termination will be the result of the criteria specified below:

1. Quality or quantity of data recording is inaccurate or incomplete
2. Poor adherence to protocol and regulatory requirements
3. Incidence or severity of adverse drug reaction in this or other studies indicates a potential health hazard to subjects

4. Plans to modify or discontinue the development of the study drug

In the event of Merck decision to no longer supply study drug, ample notification will be provided so that appropriate adjustments to subject treatment can be made.

4 Study Drugs

4.1 Description, Supply and Storage of Investigational Drugs

4.1.1 Investigational Drug Tamoxifen

Tamoxifen is available in the following doses for oral administration.

- 10 mg Tablets. Each tablet contains 15.2 mg of tamoxifen citrate, which is equivalent to 10 mg of tamoxifen.
- 20 mg Tablets. Each tablet contains 30.4 mg of tamoxifen citrate, which is equivalent to 20 mg of tamoxifen.

The administered dose will be 20 mg daily.

Classification

Non-steroidal anti-estrogen

Mechanism of Action

Following a single oral dose of 20 mg tamoxifen, an average peak plasma concentration of 40 ng/mL (range 35 to 45 ng/mL) occurred approximately 5 hours after dosing. The decline in plasma concentrations of tamoxifen is biphasic with a terminal elimination half-life of about 5 to 7 days. The average peak plasma concentration of N-desmethyl tamoxifen is 15 ng/mL (range 10 to 20 ng/mL). Chronic administration of 10 mg tamoxifen given twice daily for 3 months to patients results in average steady-state plasma concentrations of 120 ng/mL (range 67-183 ng/mL) for tamoxifen and 336 ng/mL (range 148-654 ng/mL) for N-desmethyl tamoxifen. The average steady-state plasma concentrations of tamoxifen and N-desmethyl tamoxifen after administration of 20 mg tamoxifen once daily for 3 months are 122 ng/mL (range 71-183 ng/mL) and 353ng/mL (range 152-706 ng/mL), respectively.

After initiation of therapy, steady state concentrations for tamoxifen are achieved in about 4 weeks and steady-state concentrations for N-desmethyl tamoxifen are achieved in about 8 weeks, suggesting a half-life of approximately 14 days for this metabolite. In a steady state, crossover study of 10 mg NOLVADEX tablets given twice a day vs. a 20 mg NOLVADEX tablet given once daily, the 20 mg NOLVADEX tablet was bioequivalent to the 10 mg NOLVADEX tablets.

Metabolism:

Tamoxifen is extensively metabolized after oral administration. N-desmethyl tamoxifen is the major metabolite found in patients' plasma. The biological activity of N-desmethyl tamoxifen appears to be similar to that of tamoxifen. 4-Hydroxytamoxifen and a side chain primary alcohol derivative of tamoxifen have been identified as minor metabolites in plasma. Tamoxifen is a substrate of cytochrome P-450 3A, 2C9 and 2D6, and an inhibitor of P-glycoprotein.

Excretion:

Studies in women receiving 20 mg of ¹⁴C tamoxifen have shown that approximately 65% of the administered dose was excreted from the body over a period of 2 weeks with fecal excretion as the primary route of elimination. The drug is excreted mainly as polar conjugates, with

unchanged drug and unconjugated metabolites accounting for less than 30% of the total fecal radioactivity.

Drug-drug Interactions:

In vitro studies showed that erythromycin, cyclosporin, nifedipine and diltiazem competitively inhibited formation of N-desmethyl tamoxifen with apparent K₁ of 20, 1, 45 and 30 μM, respectively. The clinical significance of these in vitro studies is unknown.

How Supplied:

Tamoxifen (generic) is commercially available. (AstraZeneca has discontinued the commercial manufacture and distribution of branded NOLVADEX® tablets in the United States as of June 2006)

Contraindications:

Tamoxifen is contraindicated in patients with known hypersensitivity to the drug or any of its ingredients.

Complete and updated adverse event information is available in the Investigational Drug Brochure and product package insert.

4.1.2 Investigational Drug Vorinostat (Zolinza, NSC 701852)

Vorinostat is available in size 3 capsules containing 100 mg of Vorinostat for administration.

Classification

Antineoplastic

Mechanism of Action

Vorinostat, a histone deacetylase (HDAC) inhibitor. Histone deacetylases (HDACs) are a family of enzymes that regulate chromatin remodeling and gene transcription via the dynamic process of acetylation and deacetylation of core histones.

Vorinostat, a potent inhibitor of HDAC activity, binds directly to the catalytic pocket of HDAC enzymes. It causes G1 or G2 phase cell-cycle arrest, apoptosis, or differentiation in cultured transformed cells

Storage:

Store vorinostat capsules at room temperature, 15 to 30 .C (59 to 86 .F). Do not store above 30.C. Avoid exposure to excessive moisture.

Method of Administration:

Unless otherwise stated in the protocol, vorinostat capsules must be administered whole. Administer doses of vorinostat with food, if possible.

Potential Drug Interactions:

The major pathways of vorinostat metabolism involve glucuronidation and β-oxidation. As vorinostat is not eliminated via CYP450 pathways, no drug-drug interactions are expected with known CYP450 inhibitors or inducers. Although vorinostat was not a potent reversible CYP450 inhibitor, studies performed to monitor gene expression changes indicated some potential for CYP2C9 and CYP3A4 activity suppression. However, these changes were observed at concentrations higher than the pharmacologically relevant concentration of 2 μM (C_{max}). Prothrombin time and INR prolongations have been reported in patients taking vorinostat concomitantly with coumarin derivative anticoagulants. Monitor these patients more frequently for alterations in their coagulation parameters.

Special Handling:

Vorinostat is an anticancer drug. If clean powder is spilt from broken or damaged vorinostat capsules care should be taken to minimize inhalation or direct contact with skin. Wash spill area at least 3 times with ethyl alcohol, followed by water.

Patient Care Implications:

Because vorinostat's dose limiting toxicities are anorexia, dehydration, diarrhea, and fatigue, patients should maintain adequate fluid and food intake. Encourage patients to seek a nutritional consult. Treat diarrhea promptly with appropriate supportive care, including loperamide. Instruct patients to begin taking loperamide at the first signs of: 1) poorly formed or loose stool, 2) occurrence of more bowel movements than usual in one day, or 3) unusually high volume of stool. Loperamide should be taken in the following manner: 4 mg at first onset of diarrhea, then 2 mg after each unformed stool. Daily dose should not exceed 16 mg/day. Loperamide should not be taken prophylactically. Advise patients to drink plenty of clear fluids to help prevent dehydration caused by diarrhea. Avoid loperamide if there is the presence of blood or mucus in the stool or if diarrhea is accompanied by fever. If grade 3 or 4 diarrhea develops, discontinue further treatment with vorinostat. Patients should not have taken valproic acid, another histone deacetylase inhibitor, for at least 2 weeks prior to study enrollment.

How Supplied:

Vorinostat is supplied by Merck & Co., Inc. Vorinostat will be provided in a 100-120 tablet bottle. For the purpose of this study, vorinostat will be given at 400 mg per day (4x 100 mg tablets), 5 of 7 days. Please refer to complete prescribing information in the FDA packet insert for storage and handling.

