5.1.1 Dose Modifications and Dosing Delays

The following dose modification rules will be used with respect to potential toxicity. Toxicity will be assessed continuously according to the NCI Common Terminology Criteria for Adverse Events [Version 4.0 \(CTCAE v4.0\)](#)

The following dose modifications should be made for febrile neutropenia, and blood counts obtained on day one of each cycle. If more than one of these conditions applies, use the most stringent (i.e., the greatest dose reduction). **The AE may be due to pembrolizumab or**

vorinostat alone in which case the respective agent should be reduced. If overlapping toxicity is suspected both drugs may be reduced with the potential to re-escalate the non-offending agent. Given the very different nature of pembrolizumab and vorinostat/tamoxifen toxicities, separate tables are shown for individual agents.

No dose modification will be pursued for tamoxifen.

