diarrhea is accompanied by fever. If diarrhea is suspected to be linked to pembrolizumab and is \geq grade 3, hold dose until toxicity resolves to \leq grade 1, then resume at dose given in prior cycle.

Other Non-hematological Toxicities:

Laboratory abnormalities must be clinically relevant and dose and drug related to prompt dose modifications.

Give the following dose based on the worst toxicity encountered during the previous cycle:

Fatigue	Vorinostat	Tamoxifen
Grade 1	100%	100%
Grade 2	Hold until toxicity is \leq grade 1, then resume at dose given in prior cycle.	100%
Grade 3, 4	Hold until toxicity is \leq grade 1, then resume at 75% (or less) of dose given in the prior cycle. If grade 3 toxicity recurs despite dose reduction, decrease to 50 % of initial dose.	100%.

Other	Vorinostat	Tamoxifen
Grade 1	100%	100%
Grade 2	Hold until toxicity is \leq grade 1, then resume at dose given in prior cycle.	100%
Grade 3	Hold until toxicity is \leq grade 1, then resume at 75% (or less) of dose given in the prior cycle. If grade 3 toxicity recurs despite dose reduction, decrease to 50 % of initial dose.	100%
Grade 4	Discontinue protocol therapy.	100%

Vorinostat may be reduced for grade II fatigue, asthenia, weight loss or other constitutional symptoms if deemed in the best interest of the patient.

Effects on the Eye: Ocular disturbances, including corneal changes, decrement in color vision perception, retinal vein thrombosis, and retinopathy has been reported in patients receiving tamoxifen. An increased incidence of cataracts and the need for cataract surgery have been reported in patients receiving tamoxifen. If grade 3 or 4 ocular toxicities occur, both drugs should be stopped. Any rechallenge should be discussed with the study chair.

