In addition to the interim analysis for efficacy that is built into the Simon 2-stage design (see above), in each arm we will evaluate the need for dose modification after 6 patients have been enrolled. If 2 or more patients have a grade 3 non-hematologic toxicity that is clearly related to pembrolizumab, this agent will be reduced to 75%. Dose modification of vorinostat should be undertaken as per dose modification guidelines, a prior study with vorinostat and tamoxifen suggest that there is a high interpatient variability and tolerance and vorinostat will be adjusted per dose modification guidelines individually.

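### Grade 3 diarrhea carries two different vorinostat instructions, and the pembrolizumab resume rule for linked diarrhea reaches grade 4 and is not separated from the enterocolitis stop rule

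*Combined protocol and SAP*

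**What the plan says.** **Vorinostat.** Section 4.1.2, under Patient Care Implications, gives loperamide advice and then an unconditional stop: "If grade 3 or 4 diarrhea develops, discontinue further treatment with vorinostat". Section 5.1.1 opens with "The following dose modification rules will be used with respect to potential toxicity", and section 8.2 (Interim Analyses) relies on such rules: "Dose modification of vorinostat should be undertaken as per dose modification guidelines". The diarrhea paragraph in section 5.1.1.1 repeats the loperamide advice without the vorinostat stop. Fatigue has its own table there and diarrhea does not. The table headed 'Other' has columns for vorinostat and tamoxifen only. Its grade 3 row holds vorinostat until grade 1 or less, "then resume at 75% (or less) of dose given in the prior cycle", with a further cut to half the initial dose on recurrence. Its grade 4 row reads "Discontinue protocol therapy".

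**Pembrolizumab.** The same diarrhea paragraph adds: "If diarrhea is suspected to be linked to pembrolizumab and is" at or above "grade 3, hold dose until toxicity resolves to" grade 1 or less, after which the previous cycle's dose resumes. Sections 5.1.1.2 and 6.3.4, under a bullet also headed 'Diarrhea', list diarrhea as a sign of enterocolitis. They stop pembrolizumab permanently and start steroids for grade 3 enterocolitis, and withhold it at grade 2. They ask for infection to be ruled out and for endoscopy to be considered. Grade 4 is not mentioned. For continuing treatment they refer to section 5.2.

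**The concern.** Section 4.1.2 names diarrhea as a dose-limiting toxicity of vorinostat, and section 5.1.1.2 treats it as a possible sign of enterocolitis on pembrolizumab. Every arm in Table 5.1 combines the two drugs, so attributing an episode to one of them will often be uncertain. An investigator facing grade 3 diarrhea can restart vorinostat under one section while another says to stop. The same investigator can resume full-dose pembrolizumab under one paragraph, while the next subsection stops it permanently if the episode is called enterocolitis. Appendix 4 provides for participating sites, which could handle the same event differently. What is at stake is patient safety and consistent conduct.

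**Working it through.** No power or error-rate calculation applies. The check sets the rules side by side by drug and grade, and then works out the difference in dose.

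| Event | First text | Second text | Result |
|---|---|---|---|
| Vorinostat, grade 3 diarrhea | 4.1.2: discontinue | 5.1.1.1 'Other' table, by default: hold, 75% or less, then 50% | Conflict |
| Vorinostat, grade 4 diarrhea | 4.1.2: discontinue | 5.1.1.1 'Other' table: discontinue | Agree |
| Pembrolizumab, grade 3 | 5.1.1.1, linked diarrhea: hold, resume prior dose | 5.1.1.2 and 6.3.4, enterocolitis: permanent stop, steroids | Overlap, with no criterion in the protocol |
| Pembrolizumab, grade 4 | 5.1.1.1, linked diarrhea: hold, resume prior dose | 5.1.1.2 and 6.3.4: enterocolitis of this grade not named | Governed by a permissive rule |

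**Is the 'Other' table the right comparator?** This is an inference. No vorinostat row in section 5.1.1.1 is specific to diarrhea, and no other row there fits.

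**Vorinostat dose difference.** Table 5.1 gives 400 mg on 5 of 7 days in a 21-day cycle.
- Dosing days per cycle: 3 weeks × 5 = 15.
- Full dose: 400 mg × 15 = 6000 mg.
- After a first grade 3 event, 75% of 400 mg = 300 mg: 300 mg × 15 = 4500 mg at most.
- After recurrence, 50% of 400 mg = 200 mg: 200 mg × 15 = 3000 mg.
- Under section 4.1.2: 0 mg.

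**Pembrolizumab dose difference.** 200 mg every 3 weeks if the episode is handled as linked diarrhea, against 0 mg if it is called grade 3 enterocolitis.

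**Does the text elsewhere separate diarrhea from enterocolitis?** Section 5.1.1.2 describes a work-up but ties no finding to either action. Section 5.2 contains no diarrhea or enterocolitis rule, and section 5.2.2 lists only overdose and liver tests. By contrast, the infusion-reaction table and the pneumonitis table (5.12) both name grade 4 and stop pembrolizumab there. This suggests that the missing grade in the enterocolitis bullet is an oversight.

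**The case against.** **The protocol has a tie-break.** Section 5.1.1 says to apply the most stringent modification when several conditions apply. A reader could add that a diarrhea-specific rule outranks a residual table, so the answer is to stop vorinostat. That is a sensible reading. But the sentence follows one about febrile neutropenia and day-one blood counts and concerns coexisting conditions; it does not clearly choose between two rules for one event. The line in section 5.2 about the system with the greatest toxicity ranks organ systems. The attribution text in section 5.1.1 says which drug to adjust, not which vorinostat rule to use.

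**Grade 4 pembrolizumab is covered.** This stands in part. A reader might infer that the protocol has no pembrolizumab rule for grade 4 diarrhea. The text does not support that, because the resume sentence covers grade 3 and above. The weakness is that the rule is too permissive. Many clinicians would also read the stop for grade 3 enterocolitis as including worse cases, but the text does not say so. The grade 4 entry "Discontinue protocol therapy" does not settle it either: it sits in the vorinostat column, tamoxifen stays at 100%, and section 5.1.1 notes that "separate tables are shown for individual agents".

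**The boundary may be defined elsewhere.** Section 3.1 says pembrolizumab is modified under Merck guidelines, and sections 5.1.1.2 and 5.1.1.3 cite a separate guidance document on immune-related events. These were not supplied and may answer the pembrolizumab question. Nothing in the protocol says that they override its own sentences. This objection stands as a limit on confidence.

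**Other safeguards exist.** Section 3.4 ends treatment for unacceptable adverse events, section 6.2.3 allows withdrawal on judgment, section 6.1 stops pembrolizumab on recurrence after re-challenge, and section 7.8 provides committee review. They reduce the risk. However, the first two rest on judgment, the third acts only after re-exposure, and review does not say which dosing rule applies.

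**Conclusion.** The point holds, as a patient-safety wording defect that should be fixed. For vorinostat, grade 3 diarrhea leads either to a stop or to a restart at up to 4500 mg per cycle, and nothing in the text clearly chooses. Confidence is high, on the assumption that diarrhea falls under the 'Other' table. At grade 4 there is no vorinostat conflict.

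For pembrolizumab, the text as written lets the prior dose resume after linked diarrhea of grade 3 or higher, including grade 4, and does not say when such an episode counts as enterocolitis. Confidence is moderate, because the Merck guidance was not available.

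A reader might also infer harm to the toxicity endpoint, the 24-week response status or the Simon design. The documents do not support that: they give no diarrhea rate for this combination and nothing that links the wording to those results. Nor should every doubtful section pointer be counted as a failed diarrhea rule. Only the pointer to section 5.2 sits in the enterocolitis text, and it stands in the grade 2 bullet.

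**What to change.** 1. In section 5.1.1.1, add a vorinostat row for diarrhea that says discontinue at grade 3 or 4, matching section 4.1.2, and state that it overrides the 'Other' table. If the clinical team prefers hold-and-reduce at grade 3, amend section 4.1.2 instead; what matters is one rule.
2. In the enterocolitis stop rule in sections 5.1.1.2 and 6.3.4, change grade 3 to grade 3 or 4.
3. Limit the pembrolizumab resume sentence in section 5.1.1.1 to grade 3 diarrhea not judged to be enterocolitis after the work-up in section 5.1.1.2. Take the criterion for that judgment from the Merck guidance, or state it if the guidance has none. Say explicitly what applies to grade 4 diarrhea not called enterocolitis, so that the limit leaves no new gap.
4. Correct the pointer to section 5.2 so that it leads to the rule on continuing pembrolizumab.

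The by-grade layout of Table 5.12 for pneumonitis is a ready model. The cost is amendment wording, notice to investigators and possibly a few more drug discontinuations.
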